### **9.3.2 User Permissions**

Prior to initial site rollout, all sites will provide a list of authorized users designated by 'view only' or 'view and edit'. Patient navigators will be given highest level permissions in order to ensure that they can input patients, and run reports as needed. Navigator supervisors and any staff who provide coverage for navigators will also have full view and edit permission. Because the goal of the registry is to quickly allow navigators to coordinate care when patients move between hospitals, all navigators and supervisors will have access to all records in the registry. Other clinical providers (e.g., nurses, physicians, social workers) at the hospitals may request access to view the registry. After training, these clinicians will be granted view only status only of patients receiving care at their hospital site, to ensure that only individuals with active clinical roles in patient care will have access to the registry.

Any changes to the site permissions list should be sent to the TRIP project team and will be updated in the system by BMC IT personnel responsible for assigning REDCap access.

### **9.3.3 Data elements**

The data elements included in the registry are the minimum information needed by navigators to actively manage and support their patients, assist them in keeping clinical appointments, and address the social determinants that often result in patients delaying or falling out of clinical care. Therefore the registry will not have extensive clinical information about the type of cancer, specific types of treatment, medications, comorbidities or complications of care. Additionally, only MRN, patient first and last name, date of birth, phone number, and study eligibility criteria are required, all other fields are optional, and navigators will be the only individuals entering data in these fields. The registry will include the following categories of data elements:

1. Patient demographics – Sufficient demographic information to uniquely identify women in the data base, including first and last name, date of birth and medical record number from each hospital system where a patient receives care. Preferred language, race/ ethnicity and gender identification fields will be available to assist navigators identify patients and their needs. A free text field will allow navigators to input specific biographical data which will help in the care of the patient (such as background, family structure, hobbies).
2. Minimal clinical information necessary for navigators to conduct their work. This will include stage of diagnosis and date of diagnosis, as this information will help navigators focus on meeting clinical benchmarks including first surgery within 45 days and first treatment within 60 days. It will also include insurance and a free text field to document any insurance restrictions/ need for prior authorizations, etc.
3. Patient contact information – detailed information to assist navigators in communicating with patients, including address, phone numbers, email, and social media as appropriate

4. Family/ secondary contact information – detailed information on 2 – 3 individuals the navigator can contact in event of emergency or patient not keeping appointments, including phone, email.
5. Patient navigator information– who is the navigator for the patient, and contact information for navigator and his/her supervisor
6. Referral source – how patient was referred to navigator and specific concerns that prompted referral
7. Provider information – for each medical provider involved in care, their name, hospital, and best methods to reach them or their clinical team. This may include a best contact of a nurse or patient coordinator who works with the provider.
8. Appointments – a listing of all medical appointments, including office visits, infusions, surgeries, radiation oncology visits, imaging studies will be listed by type of appointment, location, provider, and date and time. The outcome of each appointment (attended, rescheduled, cancelled) can be documented.
9. Navigator contacts with patients – the registry will include fields to document the date and time, type of contact (e.g., in person, phone, SMS message, email), duration and outcome of contacts with patients. Free text fields will allow navigators to note additional information as necessary.
10. Social Needs information—the registry includes fields for the navigator to indicate when a systematic assessment for social needs was conducted, the reason for doing the assessment, the type of assessment used (TRIP instance of Aunt Bertha or other validated tool, such as the THRIVE instance of Aunt Bertha at BMC), whether any needs were identified as a result of the assessment, and whether any referrals were made for the patient to address identified needs.

All entries into the registry will be time and date stamped, and will indicate which user entered the data.

Navigators can add information into the registry as frequently as is required depending upon the number of follow-up visits necessary, and the amount of contact the navigator has to support the patient through their care. This will be determined on a per patient basis, as it will likely vary from patient to patient.

#### **9.3.4 Patient Identification**

Navigators will identify patients in 2 ways: 1) using their standard methods as part of their clinical workflow. The majority of patients will be identified via physician or social worker referral at the clinical site of origin, or through discussion of the case in the Breast Cancer tumor board or case conference. 2) using a potential patient list provided by their site's IT/Research Administration to review patients that match eligibility criteria prior to an upcoming scheduled oncology appointment.

As part of the TRIP intervention, patient navigators at each of the 6 clinical sites are responsible for identifying eligible patients based on the aforementioned eligibility criteria. In order to facilitate effective identification of eligible patients as part of each navigator's workflow, the TRIP

team is collaborating with Information Technology personnel at each clinical site to produce a potential patient report. At each individual site, these reports will be generated weekly from electronic medical records and produce a list of patients who meet the following criteria:

1. A scheduled visit for a diagnosis of breast cancer in the next one to two weeks
2. A ZIP code within a 35 mile radius of Boston
3. Other key eligibility criteria (non-white, non-English speaking, and/or uninsured/public insurance)

The PHI data included in these reports are patient name, MRN, appointment type, provider, race/ethnicity, primary language, ZIP code, and insurance (if available). These reports are unique to each site and are accessible locally via secure folder or encrypted email by a patient navigator and in some cases, study team personnel at their site.

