### 5.1.4 Study subjects

All adult females (18 years or older) with a new breast cancer diagnosis receiving or planning to receive care at a participating site during the study period will be eligible for inclusion if they have a residential ZIP code within a 35 mile radius of Boston and have any of the following risk factors for delays in care: are Black and/or Hispanic ethnicity, speak Non-English as their primary language, and/or have only public or no form of health insurance. Based on MA Cancer Registry statistics, **1,300** study subjects are expected over the study period (633 controls, 667 intervention) as outlined below in table 6.

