# **7 Study Subject Selection**

## **7.1 Subject Inclusion Criteria**

In order to be eligible to participate in this study, an individual must meet all of the following criteria:

Eligibility criteria: All women with breast cancer diagnosed during the study period will be eligible for inclusion if they meet three study criteria:

1. are an adult female 18 years of age or older;
2. reside within a 35 mile radius of Boston;
3. have any of the following risk factors for delays in care:
  - a. Black and/or Hispanic race/ethnicity
  - b. do not speak English as their primary language and/or
  - c. have only public insurance or are uninsured at the time of diagnosis.

Women who do not meet all three criteria will be excluded from the study. In some cases it is possible, due to the scope of the patient navigator's responsibilities that patients who are ineligible will be entered into the Registry. As the registry is HIPAA compliant and these individuals will be excluded from compiled data sets, the study team does not perceive this to be a major risk.

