#### **10.1.5 Data Source: Electronic Health Records**

Treatment data elements will be manually abstracted for both historical control and intervention subjects from **Electronic Health Records (EHR)** at each site. Abstraction from the EHR will be conducted by a trained Research Assistant employed by that site and overseen by the site PI. Data elements from EHR abstraction will be uploaded or entered directly into the TRIP REDCap abstraction project. For more information, see *Figure 1 Table 1*.

**Intervention patients:** Potential Patient Lists will be generated locally at each participating institution to aid Patient Navigators in identifying potentially eligible patients with new breast cancer diagnoses. Every week, Patient Navigators will receive a list of patients who meet TRIP eligibility criteria and have an upcoming appointment for the following week. These lists will be generated by the EHR via a script developed by each site's IT department or research administration group and uploaded to a secure folder on the Patient Navigator's local drive or sent locally through secure email.

**Historical Controls:** Historical controls will be identified by working with each site's tumor registrar to generate a list of all breast cancer patients during the historical time period. These data will be securely stored locally at each site, and transmitted to the TRIP study team at BMC via secure Box.com folder, SFTP, or secure email. The data will then be saved to the secure tripdata\$ folder. These data will be reviewed by the TRIP data analyst to ensure completeness and correct formatting of files, and to exclude all ineligible patients according to TRIP eligibility requirements. Then the TRIP data analyst will upload the eligible patients' data to a secure REDCap project for chart abstraction. This REDCap project will be used to store clinical data manually abstracted from each EHR, and entered by the site's Research Assistant.

Historical control datasets will include the following variables requested from each site:

- a. First Name
- b. Last Name
- c. MRN
- d. Sex
- e. Race/ethnicity
- f. Date of diagnosis
- g. Date of birth

- h. ZIP code at diagnosis
- i. Primary institution
- j. Primary payer at diagnosis
- k. Date of last contact or death

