**Figure 1 Data Sources and Codification Procedure**

**Table 1. Overview of Patient Identifying Elements**

Data Source	Description	Access	Purpose of data	PHI data elements
HIPAA Compliant REDCap Registry	A tool to support the daily work of Patient Navigators to manage their active caseload and share information with Navigators when they transfer their care to another institution in the TRIP program. Use of the registry is considered a standard part of the Navigator's workflow.	Patient Navigators across all 6 sites, Select members of the TRIP program team (all IRB approved and compliant)	Implementation data: will determine if the standard of care navigation protocol was administered	
 
• Intake date
 
• MRN
 
• Patient Name
 
• DOB
 
• Address
 
• Phone number
 
• Email
 
• Appointment dates
 

HIPAA Compliant Aunt Bertha Platform	A tool to support the daily work of Patient Navigators to systematically screen patients for barriers to care and identify local resources to help them overcome those barriers. Use of the platform is considered a standard part of the Navigator's workflow.	Patient Navigators across all 6 sites, Select members of the TRIP program team (all IRB approved and compliant)	Implementation data: will determine if the standard of care navigation protocol was administered	
 
• Patient Name
 
• Email
 
• Phone Number
 
• Zip Code
 
• Date Social Needs Assessment Completed
 

Electronic Health Record-Potential Patient List	Automated list of patients scheduled for breast cancer care in the coming week is generated by the Site. Another tool for Navigators to identify who needs their services. Use of the list is considered a standard part of the Navigator's workflow.	Site Specific Navigators, Select members of the TRIP program team (all IRB approved and compliant)	Implementation data: will determine if the standard of care navigation protocol was administered	
 
• MRN
 
• Zip code
 
• Patient Name
 
• Race
 
• Date of visit
 

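### The weekly patient list in section 9.3.4 filters on non-white race instead of Black and/or Hispanic, so read literally it omits one small eligible subgroup, in the intervention arm only

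*Combined protocol and SAP*

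**What the plan says.** Eligibility requires any one of three risk factors. Section 7.1 gives the first as "Black and/or Hispanic race/ethnicity"; the second is a primary language other than English; the third is to "have only public insurance or are uninsured at the time of diagnosis". Section 5.1.4 repeats the set: women who "are Black and/or Hispanic ethnicity, speak Non-English as their primary language, and/or have only public or no form of health insurance". The Protocol Summary (section 2) agrees.

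Section 9.3.4 describes a weekly report that each site draws from its electronic records to help navigators find eligible women. Besides an upcoming breast cancer visit and a ZIP code in range, its filter is "Other key eligibility criteria (non-white, non-English speaking, and/or uninsured/public insurance". Section 10.1.5 describes the same product differently: navigators "receive a list of patients who meet TRIP eligibility criteria". Section 10.3.3 also says that the report matches eligibility criteria.

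The list is not the main route. Section 9.3.4 states: "The majority of patients will be identified via physician or social worker referral at the clinical site of origin", or through tumor board or case conference. It also makes navigators responsible for applying the stated eligibility criteria. Section 9.1 adds review of pathology reports and manual review of physician schedules.

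Controls are found another way. Under section 10.1.5 the tumor registrar lists all breast cancer patients in the historical period, and the data analyst removes those who do not meet TRIP eligibility.

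**The concern.** Non-white is not the same set as Black and/or Hispanic. A woman recorded as White race and Hispanic ethnicity meets criterion 3a but is not non-white on a race field. An Asian woman is non-white but does not meet criterion 3a. The filter and the eligibility rule therefore cannot both describe the same list.

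What is at stake is comparability of ascertainment. Under section 2, eligible women diagnosed after a site starts belong to the intervention arm. Section 5.1.5 expects all of them to be enrolled, and section 12.3 invokes intention to treat. But section 5.1.6 has treatment data abstracted only for intervention women who are enrolled. An eligible woman whom nobody identifies belongs to the arm by design yet contributes no outcome, while her counterpart in the control period is found through the registrar. She may also miss navigation, although the protocol names her group as at risk of delay.

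No section describes a step that recovers missed eligible women. The monitoring in section 10.2.3 looks at enrollment goals and at whether enrolled women are eligible. The adjustment in section 12.3 cannot restore women who were never abstracted.

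**Working it through.** The plan gives no figure on this point to reproduce. The check compares the two rules over every combination of characteristics, then gives a range for the size.

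**Step 1: the rules.**
- Protocol rule (7.1): Black OR Hispanic OR non-English primary language OR public-only/uninsured.
- List rule, read literally (9.3.4): race not White OR non-English OR public/uninsured.

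The list's insurance branch does not say public *only*. I treat the two insurance branches as the same, so that the comparison isolates the race term.

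**Step 2: enumeration.** Three race groups (White, Black, Asian/other), Hispanic yes/no, English yes/no, and public/none versus private insurance give 3 × 2 × 2 × 2 = 24 combinations. The rules disagree in two:

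| Race | Hispanic | Language | Insurance | Eligible (7.1) | On list (9.3.4) |
|---|---|---|---|---|---|
| White | Yes | English | Private | Yes | No |
| Asian/other | No | English | Private | No | Yes |

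Because the factors are alternatives, a White Hispanic woman whose primary language is not English, or who is recorded as public-only insured or uninsured, is still listed. Section 9.3.4 says the report carries insurance only where available. If that field is blank, a publicly insured, English-speaking White Hispanic woman could also drop out.

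**Step 3: consequence of each disagreement.**
- Listed but ineligible: section 7.1 excludes such women from compiled data. The cost is navigator workload, not bias.
- Eligible but not listed: recovered only if another route finds them.

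**Step 4: size.** The intervention total comes from Table 6 (section 5.1.4): 224 + 128 + 104 + 108 + 39 + 64 = 667. The subgroup's share is not in the documents. I assume *f* = 1% to 10%, and let *c* be the fraction found by other routes, also an assumption.

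Women missed = 667 × *f* × (1 − *c*)

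| *f* | *c* = 0 | *c* = 0.5 | *c* = 0.9 |
|---|---|---|---|
| 1% | 6.7 | 3.3 | 0.7 |
| 5% | 33.4 | 16.7 | 3.3 |
| 10% | 66.7 | 33.4 | 6.7 |

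The range is about 7 to 67 with no other route working, and about 1 to 7 if other routes find 90%.

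**Step 5: effect on the plan's numbers.** Even at the extreme, 1,300 − 67 = 1,233 women remain, above the 1,008 that section 12.2 requires. The issue is comparability, not sample size.

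**The case against.** The strongest reply is that the list is not the gate. By section 9.3.4 it comes second to referral and case discussion. Two of the further routes in section 9.1, pathology review and schedule review, need neither a referral nor the list. Navigators are told to apply the actual criteria. This stands, and it is why the upper figures should be read as a ceiling.

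A second reply is that non-white may be loose shorthand. It sits in a parenthesis glossing eligibility, the report carries a combined race/ethnicity field, and no query specification or coding is given. This also stands: whether any site programmed a race-only filter cannot be established. But each site writes its own script (section 10.1.5), so undefined wording can be coded six ways, which is itself a reason to define it.

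Three stronger readings are tempting and not supported:
- A reader might infer that White Hispanic women as a group are absent from the intervention arm, so that the arms represent different populations. The omission is confined to one combination of characteristics, and several other routes remain.
- A reader might infer from the Overview of Patient Identifying Elements (Table 1 in section 10.1) that ethnicity is not read. Its entry for this list, described as "Automated list of patients scheduled for breast cancer care in the coming week is generated by the Site", names race alone. But that cell also omits language and insurance, on which section 9.3.4 says the list filters. It is an incomplete inventory, not a query specification.
- A reader might infer that the ineligible women on the list bias the comparison. Section 7.1 removes them.

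**Conclusion.** The point holds as a contradiction in a stated rule with a limited, one-arm consequence. The filter in section 9.3.4 conflicts with criterion 3a and with the protocol's other descriptions of the same list. Followed as written, it omits White Hispanic women who speak English and are not recorded as public-only insured or uninsured.

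The loss is probably small and cannot be sized from the documents. The ranges in the working rest on an assumed share and an assumed recovery by other routes, and on a race-only reading of non-white. No effect on the primary estimate has been shown. What makes correction worthwhile is that any loss falls on the intervention arm alone and nothing in the plan would detect it.

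**What to change.** 1. In section 9.3.4, replace non-white with Black race and/or Hispanic ethnicity, and state that the query reads both the race and the ethnicity fields at every site.
2. Once, compare intervention-period cases at each site with the tumor registrar's list, under the same eligibility filter used for controls, and abstract any eligible women who were missed. This is better than re-running the weekly report, which is built on upcoming visits. It also puts ascertainment in the two arms on the same footing, which the wording change alone does not.

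The cost is a line of protocol text, one query edit per site, one registrar extract per site for the intervention period, and a modest number of additional manual chart abstractions. For this subgroup the number would be within the range above; the comparison may also find eligible women missed for other reasons.

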### **9.3.5 Reporting**

To support the workflow, the registry will have custom reporting that will be available to both users with 'edit/view' permissions (navigators, supervisors, back-up) as well as 'view only' permissions (research staff, other clinicians). The study team plans to send weekly reports to each navigator, which will summarize patients who have been entered into REDCap and Aunt Bertha, and records that need to be reconciled. For navigators and clinicians, these may be at the patient level, navigator level or provider level. In addition, research staff can request reports at the hospital site and at the entire study level. The system will log all report requests by user and time.

### **9.3.6 Notifying a Patient Navigator a patient has transferred care**

The registry will have a messenger function allowing navigators across hospitals to communicate with each other about patients. This feature will be used when a patient:

- a) seeks a second opinion at another hospital
- b) decides to receive different treatment modalities at different institutions (e.g. Radiation at one institution, but medical oncology visits at another)
- c) decides to transfer all care to another hospital. The purpose of this feature, which we estimate will be used for 20% of cases, is to facilitate timely transitions and avoid delays in care.

### **9.3.7 Interfacing with Aunt Bertha**

In order to standardize workflow and allow for direct accessibility to the Aunt Bertha Social Needs Assessment, an 'in frame' link to Aunt Bertha will be hosted within the REDCap forms. Navigators will log into REDCap using their assigned credentials and 2-factor authentication method (confirmation via Google Authenticator app or email), complete the intake and follow-up form as necessary, and click the link to Aunt Bertha to complete the assessment for each patient.

A referring URL within REDCap will be utilized to transfer the Subject ID number, First Name, and ZIP Code into the Aunt Bertha Assessment to ensure that patients are easily identifiable for referral retrieval and data matching purposes.

### **9.3.8 Registry Training**

The TRIP Project team will provide comprehensive hands-on training to navigators and their supervisors via two required training sessions (see Patient Navigation section above for details). The initial one-on-one training on site with the navigator includes but is not limited to the following topics:

1. How to log in
2. What information is captured
  - a. Data elements and definitions
3. How to use the forms
4. Log in and demonstration of usability
5. Reporting
  - a. Sorting
  - b. Filtering

Should any major changes be made to the Registry that impact usability or navigator workflow, the TRIP team will provide follow-up training for the navigator, either via Web-ex or in-person.

